anticoagulation be reserved for patients with": 1) "non-valvular AF who present with a clear AF onset within 12 hours in the absence of recent stroke or transient ischemic attack (within 6 months)", and 2) "non-valvular AF and a CHADS2 score < 2 who present after 12 hours but within 48 hours of AF onset", and 3) "as an alternative to at least

3 weeks of therapeutic anticoagulation before cardioversion, TEE may be used to exclude cardiac thrombus".

As such, these recommendations will likely reduce the frequency of immediate cardioversions (in the emergency department), increase referrals for inpatient and outpatient TEEs, and increase hospital admissions. We propose a randomized control trial that will assess the utility of cardiac CT to improve patient access and timely care. The results of this study could have worldwide impact by improving patient quality of life and timely access to cardioversion.

Imaging to Rule Out LA Thrombus

Currently, TEE is considered the reference standard technique for the detection of intracardiac thrombus. Although the gold standard, a TEE-guided therapy is still associated with an embolic rate of 0.8%.⁹ TEE does have limitations which include: need for NPO x 6-8 hours, patient discomfort, potential complications associated with the procedure (infection, aspiration, perforation, bleeding, etc) or with sedation.¹⁰

Contrast enhanced ECG-gated cardiac CT (CCT) is a sensitive, noninvasive alternative method used to exclude of left atrial and LAA thrombus. CCT provides high spatial and good temporal resolution and its ability to detect thrombus has been evaluated.¹¹⁻¹⁵ CCT, compared to TEE, for the exclusion of thrombus in the LAA had a sensitivity and specificity of 100% and 99.3%, respectively (Table 1).¹⁶ A high sensitivity is needed to minimize risk of embolus, and if a thrombus is detected on CT, a confirmatory TEE may be performed or patients may receive anticoagulation. Some argue that the potential benefits of CT and its lower associated procedural risk, the risk:benefit ratio would still favour CT.

This research is novel because it will be the first to demonstrate in a RCT, that CT can be used as an alternative to TEE. More importantly, demonstrating that CT is cost-effective would be extremely attractive to all stakeholders given the growing financial burden of healthcare.

Hypothesis

- Primary Hypothesis: Compared to TEE, CCTA will:
 - 1. Reduce time to cardioversion for in-patients

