- Secondary Hypotheses: Compared to TEE, CCTA will:
 - 1. Reduce length of hospital or emergency room stay,
 - 2. Improve patient quality of life (QoL),
 - 3. Not increase adverse events (arterial embolism, procedural complications, bleeding),
 - 4. Have superior cost-effectiveness.

Study Objective

Overarching objective: To evaluate CCT as an alternative to TEE to expedite cardioversion, improve patient care and reduce hospital admissions for AF and atrial flutter.

- Primary Objective: To determine if CCT can reduce time to cardioversion for in-patients
- Secondary Objectives:
 - To determine if CCT can reduce length of stay (in-patient hospitalization and emergency department)
 - To determine if CCT improves patient QoL
 - o To determine if CCT is associated with fewer or more adverse events
 - To determine the specificity of CCT (in patients with filling defects and subsequent TEE)

Outcomes Measures

- 1. Time to cardioversion (Time from referral for imaging)
- 2. Hospital admission rate
- 3. Length of hospital stay (in-patient and emergency department stay)

- 4. QoL before cardioversion, at hospital discharge and at 30 days
- 5. Adverse events (embolic (arterial) event, procedural complication, major bleed (need definition))
 - a. Embolic arterial event
 - b. Procedural complication
 - c. All bleeding
 - d. Major bleeding
- 6. Operating characteristics (specificity, PPV) of CCT (subanalysis of patients receiving TEE after CCT)

Study Design

This randomized controlled trial will randomize patients undergoing cardioversion for AF or atrial flutter before 3 weeks of anticoagulation. This pilot (Vanguard) study will aim to demonstrate feasibility of enrolment and assist with final sample size calculation.

Inclusion Criteria

- Patients admitted to hospital or seen in the ED who require LA imaging prior to cardioversion
- Age ≥ 18 years old
- Able and willing to comply with the study procedures

Exclusion Criteria

- Indication for acute cardioversion (e.g. hemodynamic instability, acute coronary syndrome (ACS), or pulmonary edema)
- Unwillingness or inability to provide informed consent
- Contraindication to Cardiac CT
 - Severe renal insufficiency(GFR< 45ml/min)
 - Allergy to intravenous contrast agents
 - Contraindications to radiation exposure (for example, pregnancy)
 - Inability to perform 20-second breath-hold
- Contraindication to TEE
 - Unrepaired tracheoesophageal fistula
 - Esophageal obstruction or stricture

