 - Perforated hollow viscus
 - Poor airway control
 - Severe respiratory depression
 - Uncooperative, unsedated patient

Methods

Recruitment

Patients who meet the inclusion/exclusion criteria will be randomized to either the interventional arm (CCT) or standard of care (SOC) arm (TEE). Prior to randomization, written informed consent will be obtained from each patient. Patients will undergo imaging as per clinical routine and reports will be issued immediately.

TEE protocol

TEE will be performed as per clinical routine using multiple standard tomographic planes to rule-out LA/LAA thrombus. Echocardiographic analysis will include: LAA-emptying velocity, and grading the severity of LAA spontaneous ECHO. The severity of the SEC will be graded on a 4 point scale with 1 = minor homogeneous contrast enhancement, 2 = significant homogeneous contrast

enhancement, 3 = significant, dense, and inhomogeneous, slow-moving contrast, and 4 = dense slow-moving contrast.

Cardiac CT protocol

As per local protocol, a non-contrast enhanced prospective ECG-triggered image acquisition will be acquired. This will be followed by a contrast-enhanced prospective ECG-triggered will be acquired using a tri-phasic contrast protocols. Delayed CT images will be acquired 60 seconds after the initial contrast-enhanced CT scan.Cardiac CT image interpretation will be performed as per clinical routine. The LA and LAA will be assess for filling defects and characterized based upon attenuation values. If LA/LAA thrombus cannot be excluded, filling defects will be assessed on the delay images. Increases in attenuation would be consistent with pseudo-thrombus from 'slow flow' and 'incomplete opacification'. Areas where attenuation does not change significantly (persistent filling defect) will be diagnosed as thrombus. It will be recommended that patients with thrombus will undergo TEE.

Prevention of Bias

Enrolled patients will be processed through the usual clinical routine for patient booking and investigators will not influence timing of booking.

Duration of Follow-up

Patients will be followed for 30 days after cardioversion using electronic charts and telephone follow-up for QoL measures.

Sample Size Calculation

This pilot (Vanguard) study will aim to demonstrate feasibility of enrolment and assist with final sample size calculation.

Statistic Methods

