Statistical analyses will be performed using SAS and/or SPSS. Statistical significance will be defined as p<0.05. Continuous variables will be presented as means and standard deviations, and categorical variables will be presented as frequencies with percentages. To compare variables, the Wilcoxon rank sum or T-test will be used to compare continuous variables and Fisher's exact test for categorical variables. Costs will be calculated using Ontario Case Costing Initiative and the Ontario Schedule of Physician Fees and Benefits.

Randomization

Randomization will occur at time of referral for TEE and be performed using a random generator. Patients will be stratified according hospital location (CICU versus ward versus emergency department) and according to mode of cardioversion (electrical versus pharmacologic) and patient sex.

Ethical Considerations

The investigator will ensure that this study is conducted in full conformance with the principles of the "Declaration of Helsinki" or with the laws and regulations of the country in which the research is conducted, whichever affords the greater protection to the individual. The study will fully adhere to the principles outlined in "Guideline for Good Clinical Practice" ICH Tripartite Guideline or with local law if it affords greater protection to the patient. It is the responsibility of the investigator, or a person designated by the investigator to obtain signed informed consent from each patient prior to participating in this study after adequate explanation of the aims, methods, anticipated benefits, and potential hazards of the study. The investigator or designee will also explain that the patients are completely free to refuse to enter the study or to withdraw from it at any time, for any reason. If new safety information results in

significant changes in the risk/benefit assessment, the consent form will be reviewed and updated if necessary.

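### QoL is timed from cardioversion and discharge, which CCT is meant to bring forward, so the arms are compared at different times since randomisation and a gain from a shorter wait mostly goes unmeasured

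*Combined protocol and SAP*

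**What the plan says.** Item 4 of Outcomes Measures lists "QoL before cardioversion, at hospital discharge and at 30 days". It does not say what the 30 days are counted from. Duration of Follow-up does: "Patients will be followed for 30 days after cardioversion using electronic charts and telephone follow-up for QoL measures".

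The clock for the randomised comparison starts earlier: "Randomization will occur at time of referral for TEE and be performed using a random generator". The Hypothesis section expects CCT to "Reduce time to cardioversion for in-patients" and to "Reduce length of hospital or emergency room stay". Better QoL with CCT is a separate secondary hypothesis and a secondary objective.

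For analysis, Statistic Methods says only that "the Wilcoxon rank sum or T-test will be used to compare continuous variables". It has no adjustment for baseline or for time of assessment. The primary outcome, by contrast, runs from referral for imaging, so the protocol already has a clock common to both arms and does not use it for QoL.

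**The concern.** An outcome meant to show the effect of an assignment should be read at times that the assignment cannot move. Here the last two QoL times are set by events that the intervention is meant to advance, and the first is bounded by one of them.

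Three things follow.

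- The background ties better QoL to quicker access to cardioversion. Lining both arms up on cardioversion leaves out the waiting period, which is where that gain would arise.
- At discharge, a faster arm may be questioned on an earlier day since randomisation.
- A patient who is never cardioverted, for example because thrombus is found or rhythm reverts spontaneously, has no date from which to count 30 days.

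This is a pilot and QoL is secondary. What is at stake is mainly a QoL estimate, and a schedule, that the full trial would inherit.

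**Working it through.** The documents state no sample size, QoL instrument, effect, standard deviation or expected delay, so there is no figure to reproduce. The check is structural first, then illustrative.

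**1. The clocks.** Let randomisation be day 0, cardioversion day C and discharge day D.

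| QoL measure | Days since randomisation | Days since cardioversion |
|---|---|---|
| Before cardioversion | anywhere up to C | 0 or earlier |
| Discharge | D | D − C |
| 30 days | C + 30 | 30 |

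CCT is hypothesised to lower C and D. If it shortens the mean wait by an assumed 1 to 6 days, the TEE arm's last call falls 1 to 6 days later since randomisation, while both arms sit at exactly 30 days since cardioversion.

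**2. If QoL depends on time since cardioversion.** Assumptions, none from the documents:

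- The gain s days after cardioversion is 10 × (1 − exp(−s/τ)) points, with τ = 0.25, 1 or 7 days.
- Waits are exponential, with CCT v TEE means of 0.5 v 1.5, 1 v 3, 1 v 5 and 1 v 7 days.
- Discharge is 0.5 day after cardioversion in both arms.

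At the planned times, s is 0, 0.5 and 30 days in both arms, so the expected difference is 0 at all three, whatever the delay.

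At a fixed day d from randomisation, the expected gain with mean wait m is 10 × [1 − (m·exp(−d/m) − τ·exp(−d/τ))/(m − τ)], for m ≠ τ. Example with τ = 0.25 and d = 2: for m = 1 the gain is 10 × (1 − 0.180) = 8.20, and for m = 3 it is 10 × (1 − 0.560) = 4.40. The difference is 3.80. Selected differences (CCT minus TEE, points):

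| τ (days) | Mean wait, CCT v TEE | Planned times | Day 2 | Day 3 | Day 7 | Day 30 |
|---|---|---|---|---|---|---|
| 0.25 | 0.5 v 1.5 | 0 | 2.8 | 1.6 | 0.1 | 0.0 |
| 0.25 | 1 v 7 | 0 | 6.0 | 6.1 | 3.8 | 0.1 |
| 1 | 1 v 3 | 0 | 3.0 | 3.3 | 1.4 | 0.0 |
| 1 | 1 v 7 | 0 | 4.5 | 5.5 | 4.2 | 0.2 |
| 7 | 0.5 v 1.5 | 0 | 0.8 | 0.9 | 0.7 | 0.0 |
| 7 | 1 v 7 | 0 | 1.1 | 1.8 | 3.1 | 0.6 |

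Over all 12 combinations the ranges are 0.8 to 6.0 (day 2), 0.9 to 6.1 (day 3), 0.1 to 4.2 (day 7) and 0.0 to 0.6 (day 30). The early fixed day carries the signal. Re-dating the 30-day call alone recovers almost nothing.

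**3. If QoL instead recovers with calendar time, whenever cardioversion occurs.** There is then no waiting-time benefit to lose, but the arm discharged earlier is read earlier. The spurious difference is slope × difference in stay. Take an assumed slope of 0.1 SD per day and a two-sided 5% t-test with noncentrality δ√(n/2):

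| Stay shorter by | Spurious deficit δ | Rejection, 50 per arm | Rejection, 25 per arm |
|---|---|---|---|
| 0.5 day | 0.05 SD | 5.7% | 5.3% |
| 2 days | 0.2 SD | 16.8% | 10.7% |
| 3 days | 0.3 SD | 31.8% | 18.0% |

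Steps 2 and 3 are alternatives and must not be added together. Under step 2 the discharge difference is 0. Under step 3 it runs from negligible to material.

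**4. Baseline adjustment.** With correlation ρ between baseline and follow-up, ANCOVA multiplies the variance of the unadjusted comparison by 1 − ρ². That is 0.75 at an assumed ρ = 0.5 and 0.51 at 0.7, a reduction of 25% to 49%.

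**The case against.** The best reply is that the schedule is ordinary for a cardioversion study, that QoL is secondary in a feasibility pilot, and that the waiting benefit is already measured directly by time to cardioversion and length of stay. The first QoL measure reads naturally as a baseline, and consent already precedes randomisation. TEE's own burdens, listed in the background (fasting, discomfort, procedural and sedation risk), could affect QoL at the planned times whatever the delay.

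Much of this stands. The first measure is an ambiguity that one phrase settles, not a demonstrated error. Some QoL effect could survive the present timing. But time to cardioversion and length of stay do not test the QoL hypothesis, and nothing in the analysis section corrects for timing.

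A reader might infer three stronger things that the documents do not support.

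- **That CCT will be made to look worse at discharge by 0.2 to 0.3 SD.** That needs an assumed slope, a gap of 2 to 3 days, and QoL that does not depend on cardioversion. The last of these contradicts the argument that a cardioversion benefit is missed. The trial also enrols emergency department patients, whose stays may differ only by hours.
- **That patients never cardioverted will be dropped from the analysis.** No section says so. Their 30-day point is undefined, and losing them is a risk, not a plan.
- **That counting the 30 days from randomisation would restore the lost effect.** Step 2 of the working shows that it would not.

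**Conclusion.** The point holds in a limited form and should be acted on. As written, the plan compares QoL at different times since randomisation and mostly misses any gain that comes from a shorter wait. It also leaves patients never cardioverted without a defined 30-day QoL assessment.

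That the times differ follows from the text and the trial's own hypotheses. It rests on reading the 30 days as counted from cardioversion, which comes from Duration of Follow-up and not from item 4 of Outcomes Measures. The sizes are illustrative: 0 points at the planned times against 0.8 to 6.1 of an assumed 10 on day 2 or 3. They rest on assumed waits and recovery speed, on every patient being cardioverted, and on the same cardioversion-to-discharge interval in both arms.

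The size and direction of any bias at discharge cannot be settled from the documents, and it may be negligible. The consequence falls mainly on the design of the full trial.

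**What to change.** Rewrite item 4 of Outcomes Measures, with matching text in Duration of Follow-up and Statistic Methods:

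- Take the first QoL at consent, before randomisation.
- Replace the discharge measure with one on an early fixed day from randomisation, chosen within the expected difference in waiting time. If waits are short, day 2 or 3 serves better than day 7. With long waits and slow recovery a later day can do better, so state the expected waits and the reason for the choice.
- Date the 30-day QoL call from randomisation for every randomised patient, cardioverted or not. The purpose is a common clock and complete inclusion, not recovery of the waiting-time effect.
- Compare arms by ANCOVA adjusting for the pre-randomisation QoL. The gain in precision is separate from the timing problem.

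The number of questionnaires stays at three, and telephone contact is already planned. The cost is that the discharge form becomes a fixed-day contact, by telephone for those already home, with some risk of extra missing data. The pilot can report completion at that contact before the full trial relies on it.

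### All-cause death is in no outcome or hypothesis and length of stay has no rule for death, so an early death from an unlisted cause could be analysed as a short stay with no adverse event

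*Combined protocol and SAP*

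**What the plan says.** All references are to the combined protocol and SAP.

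- **Safety outcome.** Outcomes Measures, item 5, opens with "Adverse events (embolic (arterial) event, procedural complication, major bleed (need definition" and is then itemised 5a to 5d: embolic arterial event, procedural complication, all bleeding, major bleeding.
- **Safety hypothesis.** Secondary hypothesis 3 uses the same event types: "Not increase adverse events (arterial embolism, procedural complications, bleeding".
- **Safety objective.** The Study Objective section is general, "To determine if CCT is associated with fewer or more adverse events", and adds no event type.
- **Length of stay.** Item 3 reads in full "Length of hospital stay (in-patient and emergency department stay", with no start, end or rule for death. Secondary hypothesis 1 makes shorter better for CT: "Reduce length of hospital or emergency room stay".
- **Follow-up.** "Patients will be followed for 30 days after cardioversion using electronic charts and telephone follow-up for QoL measures".
- **Analysis.** Under Statistic Methods, "the Wilcoxon rank sum or T-test will be used to compare continuous variables and Fisher's exact test for categorical variables". There is no worst-rank, censoring or competing-event rule.
- **Population.** Randomization is stratified by "hospital location (CICU versus ward versus emergency department", so intensive-care and ward in-patients are enrolled alongside emergency patients.

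Death is named in none of these places.

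**The concern.** The trial replaces what the protocol calls the reference standard for excluding atrial thrombus with CT, in patients cardioverted before three weeks of anticoagulation. The main harm to look for is a missed thrombus. If that harm appears as a recognised embolus, item 5a counts it. If it appears as a sudden or unexplained death, it may fit none of 5a to 5d and would then be missing from the safety comparison.

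Attribution to a listed cause is a judgement, and the protocol describes neither blinding nor event adjudication. All-cause death needs no attribution.

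Length of stay adds to the problem. If stay is counted to the end of the hospital episode, the same early death becomes a short stay, which hypothesis 1 reads as benefit. The patient also has no 30-day quality-of-life value. Two secondary hypotheses could therefore look no worse, or slightly better, in an arm with more such deaths.

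**Working it through.** **1. Is death counted anywhere?** Reading the hypotheses, objectives, six outcome measures, follow-up and statistical methods together:

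- Death from arterial embolism, a procedural complication or bleeding: counted through its cause (5a to 5d).
- Death from another or unknown cause: not counted.
- Death before cardioversion: outside the follow-up window, which starts at cardioversion.
- In-hospital death in the stay comparison: no rule.

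The plan gives no sample size, death rate or stay distribution, so it has no figure to reproduce. All inputs below are assumptions.

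**2. Chance of at least one death within 30 days, any cause.** P = 1 − (1 − m)^N, where m is 30-day mortality and N is total enrolment.

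| m | N = 60 | N = 100 |
|---|---|---|
| 0.5% | 26% | 39% |
| 1% | 45% | 63% |
| 3% | 84% | 95% |

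**3. Chance of a death early enough to shorten a stay.** Only an early in-hospital death does this. If 10% to 20% of 30-day deaths fall in the first two days (assumed), the early-death risk is 0.1% (10% of 1%) to 0.6% (20% of 3%):

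- lowest: 1 − 0.999^60 = 6%
- highest: 1 − 0.994^100 = 45%

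**4. Shift in mean stay per early death.** Assume 50 per arm, log-normal stay with median 4 days and log-SD 0.7, and death spread evenly over days 0 to 2 (mean 1 day).

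- Mean stay = 4 × exp(0.7²/2) = 5.11 days.
- Shift = (1 − 5.11)/50 = −0.08 day.
- With stays spread evenly over 3 to 10 days (mean 6.5) and death at 0.5 day, the shift is (0.5 − 6.5)/50 = −0.12 day.

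**5. Shift in rank-sum z per early death, same log-normal case.**

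- SD of U = √(50 × 50 × 101/12) = 145.1.
- A typical stay exceeds half of the 50 comparators. A stay ended by death in the first two days exceeds about 4.5% of them. Shift = 50 × (0.045 − 0.5)/145.1 = −0.16. Simulation gives −0.15.
- Ranked worst, the death exceeds all 50. Shift = 50 × (1 − 0.5)/145.1 = +0.17.
- Three early deaths in one arm: about −0.46 if scored as short stays and +0.51 if ranked worst, a gap of about 1.0.

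**6. How likely is that three-death case?** With equal true risk, the chance that the arms differ by three or more deaths, over m = 1% to 3% and N = 60 to 100, is about 0.5% to 13% counting all 30-day deaths. Counting only early deaths as in step 3, it is at most about 0.5%.

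**7. What can a death comparison show in a pilot?** For 3 versus 0 deaths with 50 per arm, two-sided Fisher p = 2 × C(50,3)/C(100,3) = 2 × 19,600/161,700 = 0.24. The value of the extra outcome lies in complete reporting by arm, not in power.

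**The case against.** The case against has substance on four points.

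- **Listed causes are counted.** A reader might infer that any patient who dies early has no adverse event. The documents do not support this, because a death from embolism, a procedural complication or bleeding falls under 5a to 5d. Only other or unexplained deaths escape.
- **The end of stay is undefined.** A reader might also infer that the protocol ends the stay at death. That is the ordinary default for a stay counted to the end of hospitalisation, but the text sets no end point.
- **The stay effect is small.** The 45% to 95% chance of a death (m = 1% to 3%) covers any death within 30 days. A death after discharge does not shorten the stay, and a late in-hospital death can lengthen it. The z gap of 1.0 is an unlikely worst case, and about half of it comes from the worst-rank rule rather than from bias towards benefit.
- **Deaths may be few.** The exclusions remove patients with hemodynamic instability, acute coronary syndrome, pulmonary edema, GFR below 45 ml/min or severe respiratory depression, and emergency patients are also enrolled. No figure in the documents supports a 1% to 3% mortality.

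All four stand, and they limit the length-of-stay part. They do not answer the safety part: an unexplained death remains outside every outcome, however rare. Pilot status does not excuse it either. The study is meant to inform a larger trial, so its outcome definitions are likely to carry forward, and adding death after deaths have occurred would be post hoc.

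**Conclusion.** The concern holds in limited form. All-cause death is missing from every outcome and hypothesis, and length of stay has neither an end point nor a rule for death. An early death outside the listed causes could therefore be analysed as a short stay with no listed adverse event, and secondary hypothesis 3 could be supported despite an excess of such deaths in one arm.

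The safety omission carries the weight and depends on no numerical assumption. The length-of-stay part is a secondary, definitional point. Its size, about 0.08 day in mean stay and 0.15 in z per early death, rests on assumed arm size, stay distribution and timing of death, and would rarely alter a pilot's conclusion. This should be changed before the data are examined.

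**What to change.** **Main change.** Add to Outcomes Measures: *5e. All-cause death from randomisation to 30 days after randomisation, in every randomised patient whether or not cardioverted.* Report it by arm with Fisher's exact test, already the planned test for categorical variables, and name it in secondary hypothesis 3.

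The common window from randomisation is needed because planned follow-up starts at cardioversion. It therefore has no start for patients never cardioverted, and its timing differs between arms if CT shortens time to cardioversion, as the primary hypothesis expects. The existing 30 days after cardioversion can stay for the other outcomes.

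**Secondary change.** Define length of stay as time to discharge alive. Give in-hospital deaths the worst rank in the Wilcoxon comparison, and report the number of deaths beside it. Worst ranks have no meaning in a t-test or a mean, so this outcome should use the Wilcoxon test only. Days alive and out of hospital to day 30 is an optional alternative, not a requirement; it could blunt differences in emergency stays lasting hours.

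**Cost.** A few sentences and one more safety row. Chart review and telephone contact are already planned, but must extend to patients never cardioverted and cover the interval from randomisation. The stay result becomes slightly less favourable to an arm with deaths.

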Left Atrial imaging prior to Cardioversion: Leveraging computed tomography to rule Out Thrombus. (LA CLOT) – A Pilot Study of Hospitalized and Emergency Department Patients

Principal Investigator: [name]

Co-investigators: [name] [name], [name], [name], [name], [name], [name], [name]

Background

Atrial fibrillation (AF) is the most common cardiac arrhythmia with an estimated 12 million individuals afflicted in European Union, 5.9 million in the USA and 350,000 in Canada are affected.^{1,2} The prevalence of AF is increasing and is projected to rise in the EU to 17.9 by 2050 and 10 million people in the USA by 2060.²⁻⁴ AF and its associated complications are a growing economical burden on the healthcare system and this burden on healthcare will continue to rise.⁵

Atrial Fibrillation Guidelines

Canadian AF guidelines updated recommendations in November 2018 regarding electrical/pharmcologic cardioversion.⁶ Prior to this update, previous guideline recommendations have been:⁷

Non-anticoagulated AF/atrial flutter patients (without indication for emergent cardioversion) requiring rhythm control:

[figure not shown]
- 1) May proceed to cardioversion if non-valvular AF onset was <48hours,
- 2) If AF/atrial flutter onset is unknown or >48 hours
 - a. Anticoagulate and consider cardioversion after 3 weeks
 - b. Admit to hospital for transesophageal echocardiography (TEE) prior to cardioversion
 - c. Refer for outpatient TEE prior to cardioversion

Transesophageal Echocardiography Prior to Cardioversion

TEE is considered the reference standard to rule-out left atrial (LA) and left atrial appendage (LAA) thrombus prior to cardioversion. Several studies have examined the accuracy of TEE for detecting LAA thrombus. Compared to autopsy and intraoperative findings, TEE has a mean sensitivity of 100% and mean specificity of 99%.⁸ Klein et al. showed that TEE could be used prior to cardioversion to exclude LA thrombus with no significant increase in adverse embolic events.⁹

The new Canadian guidelines have made new recommendations (Figure) that may have downstream ramifications on resources.⁶ They have suggested that "pharmacological or electrical cardioversion of symptomatic AF or atrial flutter without at least 3 weeks of previous therapeutic

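### Follow-up is defined only from cardioversion, so randomised patients who are not cardioverted have no stated end of follow-up; and a non-significant Fisher's test would not support the hypothesis of no increase in adverse events

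*Combined protocol and SAP*

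**What the plan says.** **Follow-up.** Under Randomization: "Randomization will occur at time of referral for TEE and be performed using a random generator". Allocation therefore comes before imaging and before any cardioversion. Under Duration of Follow-up, the only rule is: "Patients will be followed for 30 days after cardioversion using electronic charts and telephone follow-up for QoL measures". Outcomes Measures, item 4, lists "QoL before cardioversion, at hospital discharge and at 30 days".

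**Routes away from prompt cardioversion.** Imaging to Rule Out LA Thrombus says that "if a thrombus is detected on CT, a confirmatory TEE may be performed or patients may receive anticoagulation". The Cardiac CT protocol section adds: "It will be recommended that patients with thrombus will undergo TEE". As background, item 2a of the guideline summary reads "Anticoagulate and consider cardioversion after 3 weeks".

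**Safety hypothesis and analysis.** Secondary hypothesis 3 is that CCT will "Not increase adverse events (arterial embolism, procedural complications, bleeding"). The matching secondary objective is two-directional: "To determine if CCT is associated with fewer or more adverse events". Statistic Methods plans frequencies with percentages for categorical variables, Fisher's exact test to compare them, and significance at p<0.05. It plans no risk difference, confidence interval or margin. Sample Size Calculation states no number of patients; the stated purpose is feasibility and help with the final sample size.

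**The concern.** **Follow-up.** The comparison is between patients as randomised, but the follow-up clock starts at an event after randomisation that need not occur. Imaging is what is randomised, and its result helps decide who is cardioverted and when. If complete follow-up depends on cardioversion, its completeness can differ between arms for reasons linked to the intervention. The patients left without a rule include those in whom thrombus was found, in whom embolism and bleeding are of particular interest.

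**Hypothesis 3.** A test of no difference can detect a difference. When it fails to do so, that is not evidence that risk was not raised. With few events, non-significance is close to assured, and a reader could take it as confirming hypothesis 3 while a several-fold rise in embolism remains compatible with the data.

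**Working it through.** **Part 1: the sections set side by side (no arithmetic applies).**

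1. Start of observation as randomised: referral for TEE (Randomization).
2. End of observation: 30 days after cardioversion (Duration of Follow-up). No other end is given anywhere.
3. Patient cardioverted, early or late: the end date and the 30-day QoL date are both defined. Nothing excludes events before cardioversion. There is no gap here.
4. Patient not cardioverted: the end date is undefined, and so is the 30-day QoL date, because item 4 of Outcomes Measures states no origin of its own.
5. Can this happen? Yes. The protocol foresees thrombus on CT leading to TEE or to anticoagulation. The inclusion criterion is a need for left atrial imaging before cardioversion, and that imaging is done to find patients in whom thrombus cannot be ruled out.

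**Part 2: what Fisher's test can say about embolism.**

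Inputs from the documents: an embolic rate of 0.8% with TEE guidance (Imaging to Rule Out LA Thrombus) and a level of 0.05 (Statistic Methods). Assumptions: 50 or 100 per arm with equal allocation (no number is stated), a two-sided test (sidedness is not stated), and a raised CCT rate of 4%, range 2% to 8%. The plan gives no power or precision figure to reproduce.

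*Power* is the sum over all (i, j) with Fisher p<0.05 of Bin(i; n, 0.008) × Bin(j; n, p), where p is the CCT rate.

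| Assumed CCT rate | 50 per arm | 100 per arm |
|---|---|---|
| 2% | 0.03% | 0.7% |
| 4% | 1.0% | 11.3% |
| 8% | 15% | 61% |

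*Smallest significant split against zero:* 6 v 0 (p=0.027 at 50 per arm, p=0.029 at 100). A split of 5 v 0 gives p=0.056 and 0.059.

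*Expected events if both arms have 0.8%:* 0.008 × 100 = 0.8 in total at 50 per arm, and 0.008 × 200 = 1.6 at 100 per arm. The probability of no embolus at all is 0.992^100 = 45% and 0.992^200 = 20%.

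*What zero events leave open:* the exact two-sided 95% upper limit for one arm is 1 − 0.025^(1/n).
- n = 50: 1 − 0.025^(1/50) = 7.1%
- n = 100: 1 − 0.025^(1/100) = 3.6%

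At 0 v 0 Fisher's p is 1, while the exact unconditional (score-based) 95% upper limit for the risk difference is 7.3 points at 50 per arm and 3.8 points at 100. These limits are about nine and five times the cited 0.8% (7.3/0.8 = 9.1; 3.8/0.8 = 4.8).

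**The case against.** **This is a feasibility pilot.** It claims no power for safety, and its objective asks about a difference in either direction, which Fisher's test fits. Nothing in the text says that a non-significant p will be read as no increase. All of this stands and keeps the point minor. It does not remove the mismatch, because the hypothesis is stated in one direction, a significance threshold is set, and no other inference is planned.

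**Stronger readings that the documents do not support.**
- *That uncardioverted patients are dropped from the safety analysis.* The follow-up sentence gives a duration and defines no analysis set, and no section excludes these patients. An imaging complication or in-hospital bleed in such a patient could still be recorded. The gap is an undefined end of follow-up and an undefined 30-day QoL date.
- *That the plan can never support hypothesis 3.* A significant result favouring CCT would support it for that category. Procedural complications are a plausible case, since the protocol expects CT to carry less procedural risk. The criticism is of non-significant results.
- *That none or one embolus is the likely outcome whether or not CCT raises risk.* At 0.8% in both arms, none or one in total has probability 81% (50 per arm) and 52% (100 per arm). At 0.8% v 4% it is 30% and 4.5%. The argument rests on low power, not on this.
- *That the three-week anticoagulation route is a trial pathway.* The quoted item belongs to a summary of previous guidelines. Study Design describes cardioversion before 3 weeks of anticoagulation, and a patient cardioverted late has a defined window in any case.

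**Conclusion.** Both parts hold, as a minor point on secondary outcomes.

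1. Complete follow-up depends on a post-randomisation event that the randomised imaging can influence, and randomised patients without that event have no stated end of adverse-event follow-up and no 30-day QoL date. The documents do not give the share affected. It is probably small, and no figure is claimed.
2. A non-significant Fisher's test does not support hypothesis 3. For embolism, that is the result to expect at 50 per arm across the assumed range and, at 100 per arm, for a rise to 2% or 4%; at 8% and 100 per arm power reaches 61%. The arm sizes and raised rates are assumptions; the 0.8% and the 0.05 level are the protocol's own. The calculations cover embolism only. Rates for procedural complications and bleeding are not given, so no power is claimed for them.

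**What to change.** **Adverse events.** Count them from randomisation to 30 days after randomisation in all randomised patients, analysed as randomised. Keep the 30-day post-cardioversion window as a second, separately reported one for those cardioverted. Both are needed: a window fixed at randomisation covers everyone but is cut short for late cardioversion (after 21 days, at most 30 − 21 = 9 days would remain). That is a limit of the added window, not a fault in the protocol.

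**QoL.** Keep 30 days after cardioversion for those cardioverted. For patients not cardioverted by day 30 after randomisation, collect QoL on that day. Report the two time origins separately and do not pool them, since which one applies depends on what happened after randomisation.

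**Hypothesis 3.** Report the risk difference (CCT minus TEE) with an exact 95% confidence interval for each adverse-event category. Reword the hypothesis as estimating that difference, in line with the two-directional objective. State that a non-significant p in the pilot will not be read as no increase.

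**Cost.** Chart review and one telephone call for the few patients not cardioverted, two windows to report instead of one, and a more modest safety claim. Clinical management is unchanged.
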